**Table 1. Guidance for Hypertension Rescue Medication Use**

Study/ Cumulative weeks	Procedure
603A weeks 1 to 6	

Follow procedures for visits 10 and 11 as early termination visits to obtain 24-h ABPM and collect safety data

Rescue medication should not be administered unless hypertensive emergency appears imminent. In those situations, refer the subject to seek urgent care in a clinic or hospital. Subject should withdraw from participation in the study and see primary care provider to start or intensify anti-hypertensive therapies

603A weeks 7 to 12	

Follow procedures for visits 5 and 6 to obtain 24-h ABPM and collect safety data

Start visit 6 (start of 603B) without rescue medication. If a hypertensive emergency appears imminent, refer the subject to seek urgent care in a clinic or hospital. Prescribe rescue medication at Visit 7 if SBP shows an increase of 30 mm Hg from baseline or exceeds 189 mm Hg in office measurements and continue study activities

603B weeks 13 to 18	

Obtain 24-h ABPM and collect safety data

Rescue medication should not be administered unless hypertensive emergency appears imminent. In those situations, refer the subject to seek urgent care in a clinic or hospital. Prescribe rescue medication at Visit 7 if SBP shows an increase of 30 mm Hg from baseline or exceeds 189 mm Hg in office measurements and continue study activities

603B weeks 19 to 24	

Obtain 24-h ABPM and collect safety data

Prescribe rescue medication if SBP shows an increase of 30 mm Hg from baseline or exceeds 189 mm Hg in office measurements and continue study activities

603B weeks 25 to 36	

Obtain 24-h ABPM and collect safety data

Prescribe rescue medication if SBP shows an increase of 30 mm Hg from baseline or exceeds 189 mm Hg in office measurements and continue study activities

Choice of rescue therapy should take into consideration current antihypertensive treatment, as well as co-morbidities, such as cardiovascular or renal disease, and severity of BP elevation. Site investigators should use their best clinical judgement when determining rescue medications.

The following strategies are recommended, but not required:

- Amlodipine should be considered first line among calcium channel blockers.
- For patients with diabetes or chronic kidney disease with proteinuria, consider addition of an ACE inhibitor or ARB, but not both in combination.
- For patients with cardiovascular disease, consider use of a beta blocker.
- For patients with volume overload, consider use of diuretics, though caution should be used if the patient is on an additional diuretic such as a thiazide.

Step down therapy: For SBP < 110 with symptoms attributable to hypotension, investigators should decrease the dose or remove the most recently added agent, at the investigator's discretion. Investigational product should be continued unless the investigator feels it is necessary to stop for the safety of the patient.

## **5.8 Restrictions**

### **5.8.1 Prior Therapy**

All subjects will continue regimens for medical conditions during the study as indicated above. No subject shall have been treated with an investigational drug within 30 days of screening or within a period equal to less than 7 half-lives of the investigational drug, whichever is longer. No subject shall have been treated with insulin or an SGLT2 inhibitor within 3 months of screening.

### **5.8.2 Fluid and Food Intake**

During the study, subjects will be counseled to remain adequately hydrated at all times. In addition, subjects should be counseled by site staff to eat a diet low in saturated fat, high in fiber, low in simple carbohydrates, and contain appropriate caloric intake to maintain weight.

Subjects will fast for approximately 8 h prior to the scheduled blood sample draws. During fasting, only water will be permitted.

### **5.8.3 Patient Activity Restrictions**

Lifestyle modification should be counseled at the screening visit. Specific recommendations will include: a) weight loss in those who are overweight or obese; b) adoption of a diet rich in fruits, vegetables and low-fat dairy products (the DASH diet) with appropriate modifications for participants with CKD; c) reduction in sodium intake to recommended levels; d) reduction of alcohol consumption to recommended levels; and e) participation in regular aerobic exercise. Patients who smoke will be encouraged to stop ([CDC guidance](#)).

## **5.9 Treatment Compliance**

Subjects will be provided with dosing instructions when the study drugs are dispensed. Subjects will also be instructed to bring their study drug with them at every visit. During the run-in period, subjects will be excluded from randomization if more than 1 day of placebo run-in medication doses has been omitted. If, in the judgement of the investigator, it was appropriate for the subject to omit these doses, this requirement may be waived.

At each visit after the start of the run-in period, the study staff will review medication use with the subject and record the drug consumption in the CRF. Reasons for non-adherence will also be recorded in the protocol deviation log if applicable.

## **5.10 Packaging and Labeling**

Investigational products will be provided to the pharmacist or designated site personnel in high-density polyethylene (HDPE) bottles of 90 tablets sealed with a child-resistant cap. A bottle of 15 bexagliflozin tablets, placebo will be provided for the 2-week run-in portion of the study. All investigational product supplies will be prepared and labeled according to the requirements of local laws and regulations. The pharmacist or designated site personnel will dispense the investigational products for each subject according to the randomization assignment.

## **5.11 Storage and Reconciliation**

Bexagliflozin tablets should be stored below 30°C (86°F). The sponsor will notify the sites of the process for returning unused drug.

## **5.12 Investigational Product Retention at Study Site**

The investigational products shall be stored in a secure area with limited access. The drug storage facility must comply with the medication storage instructions. The investigational products should be stored in a room temperature < 30°C until ready for dispensing to study subjects. The trial staff must record the amount of investigational products dispensed to each subject on the dosing record. To ensure adequate recordkeeping, subjects must bring all investigational products to each visit. The remaining tablets will be accounted for in the CRF and drug consumption forms. The procedures for obtaining drug resupply will be provided by the sponsor. All unused drug must be returned to a sponsor-designated depot after drug accountability is verified by the sponsor or its designee.

## **6 STUDY PROCEDURES**

The following sections describe procedures that are conducted in the protocol. The clinical investigator must personally conduct or supervise the procedures that are required in the protocol. The clinical investigator must personally conduct the informed consent process while other study tasks may be delegated to qualified staff after training is completed. Procedures that require clinical /medical knowledge must be performed by the investigator or qualified sub-investigators.

### **6.1 Informed Consent**

Before each subject is enrolled in the clinical study, written informed consent shall be obtained according to the regulatory and legal requirements of the participating country. As part of this procedure, the investigator must explain orally and in writing the nature, duration, purpose of the study, and the action of the drug, in such a manner that the study subject is aware of the potential risks, inconveniences, or AEs that may occur. The investigator should educate potential subjects about the scientific importance of their data and the vital role that their participation has for the outcome of the entire study. The subject must be informed that he/she is free to withdraw from the study at any time. He or she will receive all information that is required by federal regulations.

The informed consent document must be signed and dated; one copy will be given to the patient, and the investigator will retain a copy as part of the clinical study records. The investigator will not undertake any investigation specifically required for the clinical study until written consent has been obtained. The terms of the consent and the time it was obtained must also be documented.

### **6.2 Medical History**

At the initial screening visit, the investigator should review the inclusion and exclusion criteria based on the information collected at the screening visit. He or she should evaluate any change to status affecting conformance to inclusion and exclusion criteria at subsequent visits prior to randomization. At randomization, the investigator should confirm the run-in drug compliance.

### **6.3 Medical History**

The following information will be collected at the screening visit:

#### **6.3.1 General Demographics and Characteristics**

- Date of birth, age, sex, and race, and whether a female subject is of childbearing potential or not
- Significant medical and surgical history, including dates of diagnoses, procedures and whether the condition is ongoing, if applicable

### 6.3.2 Diabetes History

- Date of diabetes diagnosis
- History of all medications used to treat diabetes (to be recorded in the concomitant medication form), including start date, duration of use, and stop date, if applicable
- History of complications due to diabetes, including diabetic ketoacidosis, glaucoma, retinopathy, neuropathy, gastroparesis, nephropathy, foot ulcerations, or non-traumatic amputations, including date of diagnosis
- Frequency of hypoglycemic events (per week) that are symptomatic or require assistance

### 6.3.3 Renal and Cardiovascular Disease History

- Chronic kidney disease stage, based on KDOQI CKD classification and duration ([Appendix 5](#))
- Whether currently receiving an erythropoiesis-stimulating agent (ESA) for anemia and time of starting ESA
- History of bone disease
- History of disorders of calcium and phosphorus metabolism or hyperparathyroidism
- History of neuropathy
- History of cardiovascular diseases including hypertension, dyslipidemia, angina, congestive heart failure (including NYHA classification), known atherosclerotic cardiovascular disease, prior MI, transient ischemic attack or stroke, and prior cardiac or peripheral re-vascularization procedures. The history should include the date of diagnosis and the current status of diagnosis (resolved or ongoing).

### 6.3.4 Medication History

- Use of prescribed or non-prescribed medications, including name of medication, indications for usage, start and stop dates, dose, and frequency
- Use of supplements, including over the counter drugs, vitamins, herbal preparations, and dietary supplements within the past 30 days prior to screening. Each medication history should include the agent used, indication for usage, start and stop dates, dose, and frequency
- History of medication allergies and intolerance

## 6.4 Physical Examination

A complete physical examination shall be performed by the investigator at the time points indicated in the Schedule of Events ([Appendix 1](#)). The examination shall include a general assessment of all body systems including the skin, head, eyes, ears, nose, throat, neck, heart, lungs, abdomen, lymph nodes, and extremities.

## 6.5 Abbreviated Physical Examination

An abbreviated physical examination will include measurement of height at screening V1 only and a general assessment of the skin, heart, lungs and abdomen. The investigator will

perform abbreviated physical examinations at the time points indicated in the Schedule of Events ([Appendix 1](#)), unless clinically indicated.

## 6.6 Body Weight

Body weight will be determined in the visits indicated in the Schedule of Events ([Appendix 1](#)). The weight must be determined using a scale that is calibrated. Every effort should be made to use the same scale throughout the study duration.

## 6.7 Vital Signs

[figure not shown]
Vital signs will be measured at the time points indicated in the Schedule of Events ([Appendix 1](#)) and will include sitting, supine, and standing BP measurements, and heart rate. Only the BP measured in the seated position will be used to determine eligibility. The vital signs shall be obtained before the scheduled blood draw.

Devices designed to measure BP from the finger or wrist may not be used. BP shall be measured using an appropriately sized cuff (cuff bladder encircling at least 80% of the arm) that is applied on the upper arm at heart level. The left arm and same cuff size should be used for each measurement at all visits. If the left arm cannot be used at the screening visit or during the study for BP measurements, the reason should be documented, and the right arm should be used for BP measurements for all subsequent visits.

At each visit, BP measurements shall be obtained using a calibrated sphygmomanometer while the subject is in sitting, supine, and standing positions. Prior to measuring seated BP, the subject should be seated quietly in a chair, not an examination table, for at least 5 minutes with feet on the floor and arm supported at heart level.

A single heart rate measurement shall be taken just prior to the BP evaluation in the sitting, supine, and standing positions. Blood pressure must be taken twice with at least 2 minutes apart with the cuff fully deflated between each reading. If any of the two SBP measurements differ by more than 8 mm Hg or if any of the two DBP measurements differ by more than 5 mm Hg, a second set of 2 BP measurements should be obtained. The second set of readings should be entered into the CRF. Original and repeat readings must all be recorded in the source documents with an explanation. The average of the 2 serial blood pressure measurements will be used for the efficacy analyses.

BP will be assessed first in the seated position. After seated BP measurement has been completed, supine and standing BP will be measured to evaluate orthostatic vital signs. Supine and standing blood pressure measures will not be used to determine eligibility for the study. The subject will lie flat for 5 min and have heart rate and supine blood pressure measured using the same equipment and arm as described for seated BP. Once the supine BP measurement is complete, the subject will stand. Standing BP and heart rate will be measured after 2 min of standing. For standing BP measurements, the arm should be supported and extended such that the cuff is at heart level. The procedure for vital sign measurement is shown in Figure 2.

**Figure 2. BP Measurement Procedure**

The date, time, and all readings are to be entered into the source document and CRF for all subjects.

## 6.8 12-Lead ECG

A 12-lead electrocardiogram (ECG) shall be conducted at the time points indicated in the Schedule of Events in [Appendix 1](#) and whenever clinically indicated. This procedure should be performed in the supine position after 10 min without exertion. ECG parameters measured will be the RR interval, PR interval, QRS duration, and QT interval. Each ECG should also be assessed by the investigator for signs of ischemia, clinically significant hypertrophy, and clinically significant T-wave abnormalities or arrhythmia.

It is the investigator's responsibility to review the results of the ECG as they become available. For each abnormal ECG result, the investigator shall ascertain if the observation represents a clinically significant change from the screening ECG for that individual subject. This determination does not necessarily need to be made the first time an abnormal result is observed. The investigator may repeat the ECG to verify the original result. If the ECG result is determined to be a clinically significant and abnormal change from baseline for that subject, it is considered to reflect an AE.

## 6.9 Clinical Laboratory Tests

### 6.9.1 Laboratory Parameters

Clinical laboratory test parameters are listed in [Table 1](#).

**Table 2. List of Laboratory Tests**

---

Hematology: 

• Hematocrit (Hct)

• Hemoglobin (Hgb)

• Mean corpuscular hemoglobin (MCH)

• Mean corpuscular hemoglobin concentration (MCHC)

• Mean corpuscular volume (MCV)

• Platelet count

• Red blood cell (RBC) count

• White blood cell (WBC) count with differential

	Serum Chemistry: 

• Albumin (ALB)

• Alkaline phosphatase (ALK-P)

• Alanine aminotransferase (ALT)

• Aspartate aminotransferase (AST)

• creatinine kinase (CK)

• Blood urea nitrogen (BUN)

• Calcium (Ca)

• Bicarbonate (HCO3)

• Chloride (Cl)

• Creatinine

• Glucose

• Magnesium (Mg)

• Phosphorus

• Potassium (K)

• Sodium (Na)

• Total bilirubin

• Direct bilirubin

• Total cholesterol

• HDL-cholesterol

• LDL-cholesterol

• Total protein

• Triglycerides

• Uric acid

Urinalysis: 

• Appearance

• Bilirubin

• Color

• Glucose

• Ketones

• Microscopic examination of sediment

• Nitrite

• pH

• Protein

• Specific gravity

• Urobilinogen

	
Pregnancy test: Urine human chorionic gonadotropin (hCG) (only for females who are not diagnosed as postmenopausal)	Glycemic control 

• HbA1c

 Population PK Sampling 

• Bexagliflozin plasma level

---

## 6.9.2 Sample Collection, Storage, and Shipping

### 6.9.2.1 Hematology, Blood Chemistry, Serum Lipids, and Glycemic Control Assessments

Blood samples for hematology, chemistry, serum lipids and glycemic control assessments shall be collected. Subjects shall be in a seated or supine position during blood collection. Samples shall be collected at the time points indicated in the schedule of events in [Appendix 1](#) and [Appendix 2](#).

The study staff shall contact each subject prior to a scheduled clinic visit to confirm the time of the visit and to remind the subject of proper fasting practice. A subject must be queried to assess compliance with approximately 8 h fast prior to blood draw to ensure the lipid values can be accurately determined. If a subject has not fasted, the subject should return as soon as can be arranged to provide a specimen after proper fasting.

LDL-C will be calculated by the Friedewald equation. If triglycerides are > 400 mg/dL, the calculated LDL-C value is invalid by this equation and will be set as missing. Direct LDL-C will be determined in subjects whose triglycerides are > 350 mg/dL at the screening visit. All subsequent LDL-C of these subjects will be determined by the same direct LDL-C measurements only.

An investigator can perform additional laboratory testing to diagnose or to follow up an adverse event progression or resolution. Clinical samples should be analyzed in a local laboratory if a fast turnaround is necessary to determine the treatment plan.

#### 6.9.2.2 Urinalysis

Urine samples shall be collected routinely at designated clinic visits from a clean catch sample. Urinalysis shall be performed at the time points indicated in the schedule of events ([Appendix 1](#) and [Appendix 2](#)). Investigator or staff should document if pre-menopausal female subjects are menstruating and note it in the source documents since hematuria is likely to be identified on dipstick urinalysis.

Urine samples will be transported to the central laboratory for urinalysis. Microscopy will be conducted if the subject has a positive result on the leukocyte esterase or nitrite dipstick tests to clarify the significance of the finding. Results of glucose measurement in the urinalysis must be suppressed from the laboratory reports so the sponsor, investigators, study coordinators, pharmacists, study subjects, and the CEC members will remain blinded to the dosing assignment.

In addition, strips to assess leukocyte esterase and nitrite but not glucose will be provided for immediate assessment at the clinical sites. If more than trace positive results are shown in the leukocyte esterase and /or nitrite testing, a urine culture should be performed in a designated laboratory regardless of patient reported signs or symptoms. Results of the urinalysis and possible urine culture will be documented in the CRFs.

#### 6.9.2.3 Population PK Sampling

Blood samples for the population PK analysis will be drawn when the subjects return to the clinic during week 18 (V7) and/or week 24 (V8) from 200 subjects who consent to participating in the PK study in selected trial centers. One blood sample will be drawn at each of the 3 timepoints from each subject for a total of 3 post-dose samples per subject. Approximately 100 subjects will be sampled at 0.25 to 1 h, 7 to 10 h, and 20 to 24 h post dose (routine 1). Another 100 subjects will be sampled at 1.5 to 3 h, 3.5 to 6.5 h and 7 to 10 h post-dose (routine 2). The sampling time should take into consideration the study subject availability and can be on any of the days during the week of the specified clinical visits. The precise dosing time and sample draw time must be recorded in the CRF.

Two mL (2 mL) of whole venous blood will be collected from a peripheral vein. Samples will be placed in tubes containing K2EDTA, stored on ice, and centrifuged under refrigeration for at least ten minutes at 3,000 rpm. After centrifugation, plasma will be removed and stored frozen in 3 aliquots of 200 µL at or below -20°C. Processed frozen

plasma samples will be transferred on dry ice to the analytical laboratory and will be stored at or below  $-20^{\circ}\text{C}$  until analysis.

Plasma concentrations of bexagliflozin will be determined by a validated LC-MS/MS method. Approximately 600 measurements of bexagliflozin plasma concentrations will be collected from an estimated 200 subjects who will have received active drug in this study.

## **6.10 Dispensing Study Drug**

### **6.10.1 Run-in Drug**

The investigator or designated personnel will dispense one bottle of 15-count bexagliflozin tablets at visit 1. Prior to registering a subject in the IWRS at visit 1 to receive the designated kit numbers of run-in drug, the signed ICF and eligibility criteria required at screening visit must be confirmed.

Subjects shall be instructed to take the first dose of run-in drug at the clinic with 1 cup (~250 mL) of water. Subjects shall be instructed to withhold the study drug administration on the day of visit 2 until they are in the clinic.

### **6.10.2 Double-Blind Study Drug**

The double blind study drug shall be dispensed to the subject after the 24 h-ABPM values are retrieved and  $\geq 51$  day time and  $\geq 13$  night time BP readings are recorded successfully. The 24 h-ABPM may be repeated if necessary.

The IWRS will assign a double blind study drug kit number for each subject at visits 3, 6, and 9. The subject will be provided with a bottle of the double blind study drug and instructed to self-administer the first dose of investigational product at the clinic and to take one tablet at approximately the same time each day, before or after breakfast, with one cup (250 mL) of liquid. The day of first double blind study drug dosing is considered Day 1 of the study day. Each bottle of the investigational products will provide daily dosing for 90 days.

On the days of clinic visit, subject should not take the study drug until the visit procedures are completed.

## **6.11 Efficacy Assessments**

### **6.11.1 24-h ABPM**

ABPM will be performed for 24 hours, with measurements every 15 minutes during the day (16 h) and every 30 minutes during the night (8 h). Subjects will be fitted with the ABPM device, administer one tablet of study drug, and wear the cuff for 24 consecutive hours at the specified visit ([Appendix 1](#)). Subjects should take the study drugs while taking all their normal medications and performing normal daily activities. Subjects will be instructed to refrain from strenuous exercise or shower during this period. The ABPM device will be

placed on the arm by study staff and begin recording values immediately following the dosing.

If the ABPM is not completed or if < 64 BP readings (51 day time and 13 night time BP readings) are recorded, the procedure must be repeated. A new bottle of double blind study drug can be dispensed to a subject only after the 24 h ABPM is completed successfully.

Prior to randomization, subject who cannot complete the 24h ABPM within two attempts will be considered a screen fail. After randomization, if a subject cannot complete a 24h ABPM within two attempts, the data will be considered missing.

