## 5.4 Method of Assigning Subjects to Treatment Groups

The study will be conducted in multiple investigative sites and will involve variable numbers of subjects at each site. Enrollment will be on a competitive basis, but each site will be capped at 68 randomized subjects. Activation of investigational sites will be centrally controlled by IWRS.

Subjects who meet the eligibility criteria required at the screening visit (visit 1) must be registered in the IWRS in order to be assigned a subject number and a bottle of run-in drug. A new bottle will be assigned to the subject every 12 weeks by the IWRS at visits 3, 6, and 9. There are two randomization procedures planned in this program, at visit 3 and visit 9 ([Appendix 1](#)).

Subjects who complete the run-in period and meet the ABPM SBP  $\geq$  135 mm Hg criterion at visit 3 will be randomized to receive a bottle of bexagliflozin, 20 mg or placebo. Subjects will be assigned to each group in a 1:1 ratio. Randomization will be stratified according to diabetes status (history of diabetes or not), baseline ABPM SBP ( $\geq$  160 mm Hg or not), unmedicated or not, and renal function (eGFR  $\geq$  60 or not). The investigator or designated staff will log into the IWRS to receive the randomization code and assigned kit number for bexagliflozin tablets, active or placebo.

At visit 6 after a subject has completed the ABPM successfully, a second bottle of study drug will be assigned to the subject by IWRS. All subjects will receive active treatment for the following 12 weeks. Subjects who experience persistent hypertension during the first 12 weeks of treatment may complete visits 5 and 6 prior to week 12 as described in [Section 5.7](#).

At visit 9 after a subject has completed the 24 h-ABPM successfully, the subject will be randomly assigned to receive either active or placebo in a 1:1 ratio. A new randomization number and a new bottle of double blind study drug will be assigned and dispensed to the subject. Assignment to the active or placebo arm will be balanced to approximately equalize the representation in each arm of the following groups:

- Subjects not requiring rescue medication prior to week 24 and exhibiting a  $> 20$  mm Hg reduction in mean SBP between Day 1 and cumulative 24
- Subjects not requiring rescue medication prior to week 24 and exhibiting a  $> 5$  mm Hg and  $\leq 20$  mm Hg reduction in mean SBP between Day 1 and cumulative 24

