- Subjects not requiring rescue medication prior to week 24 and exhibiting a  $\leq 5$  mm Hg reduction in mean SBP between Day 1 and cumulative 24
- Subjects requiring rescue medication prior to week 24

If the mean SBP is missing at cumulative week 24, the subject will be withdrawn.

Subject randomization will be deactivated for all sites when the planned number of subjects is met and a minimum of 10% of the subjects have an average 24 h ABPM SBP  $\geq 160$  and  $< 180$  mm Hg at visit 3. However, if a potential subject has started the run-in period at that time and wishes to continue to participate, the subject will be allowed to continue and, if eligible, to be randomized.

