## 7 STUDY ACTIVITIES

The activities at each clinic visit listed below are presented in [Appendix 1](#). The required laboratory tests scheduled at each visit are listed in [Appendix 2](#). Detailed procedures are described in [Section 6](#).

A visit window of  $\pm 3$  days is allowed for post-randomization visits. Visit 3 is the day of randomization and the basis for the visit window. A repeat ABPM shall be performed within 2 days if the 24h-ABPM is incomplete. Only the second set of ABPM data will be entered in the case report form on visits 2-3, 5-6, 8-9, and 10-11. The other specified procedures in the same assessment period do not need to be repeated. If the ABPM fails twice at visit 3 prior to randomization, the subject is considered a screen failed subject. If the ABPM fails twice after randomization, the ABPM BP on that assessment period is considered missing.

Procedures listed for visit 10 will be completed if a subject is withdrawn from the study.

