12. CHANGE FROM ANALYSIS PLANNED IN PROTOCOL

Wilcoxon rank sum tests were added to both primary endpoints as sensitivity analysis.

Protocol specified that if < 64 BP readings (51 day time and 13 night time BP readings) are recorded, ABPM is considered as invalid and is repeated. In SAP, the validity criteria has been relax to include more subjects (section 8.1.1.1).

Additional exploratory endpoints are added in sections 4.1.3 and 4.2.3.

Baselines for efficacy endpoints are defined as the last measurement prior to the first dose of double-blind study medication, not prior to randomization per protocol. Randomization date is only used if subject is not dosed.

Adverse events occurred during 603B run-in period will not be summarized separately as stated in the protocol, instead, adverse events occurred during bexagliflozin treatment period will be summarized based on integrated safety analysis set. Some tables are only prepared for integrated safety analysis set due to lack of event occurrences.

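### Two failed week-12 ABPMs leave the visit 6 bottle under conflicting rules, and the second-set-only rule can discard a recording that the SAP would accept

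*Protocol*

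**What the plan says.** On dispensing, Protocol 6.11.1 states: "A new bottle of double blind study drug can be dispensed to a subject only after the 24 h ABPM is completed successfully". Protocol 6.10.2 sets success at 51 or more day and 13 or more night readings and names visits 3, 6 and 9. Protocol 5.4, and SAP 3.8.1 in matching words, apply the condition to the 603B bottle: "At visit 6 after a subject has completed the ABPM successfully, a second bottle of study drug will be assigned to the subject by IWRS".

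On failure, the same Protocol 6.11.1 says that after randomization "if a subject cannot complete a 24h ABPM within two attempts, the data will be considered missing"; section 7 agrees. A withdrawal rule for a missing ABPM appears only for the second randomization: "If the mean SBP is missing at cumulative week 24, the subject will be withdrawn" (Protocol 5.4). Protocol 3.1.2 starts 603B when the monitor is handed back, and 7.6 lists dispensing at visit 6; neither states a success condition.

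On repeats, Protocol 7 says "Only the second set of ABPM data will be entered in the case report form", and SAP 3.10 repeats this. SAP 6.4 takes the later of several assessments at a visit, with no check of validity. SAP 8.1.1 accepts a recording with at least 64 readings in total and either the day or the night minimum. SAP 12 explains that "the validity criteria has been relax to include more subjects".

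**The concern.** There are two linked problems.

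First, a site whose subject fails the week-12 ABPM twice has one rule that withholds the next bottle and another that calls the value missing, with no route between them. Sites may resolve this differently. If the dispensing rule is followed to the letter, a subject who could still contribute to the withdrawal study gets no drug for it because of a recording failure.

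Second, the rule that prompts a repeat can be stricter than the rule that decides validity for analysis. A first recording that the SAP would accept may be replaced by a second that it would not. The first never reaches the database, so the SAP's relaxation cannot recover it. No other ABPM is scheduled between baseline and week 12, so last observation carried forward (SAP 8.1) normally has nothing to carry, and the subject has no 603A primary value. The same CRF rule applies to the week-24 and week-36 recordings.

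**Working it through.** **1. Does 603B use the week-12 ABPM?**

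- Balancing groups at the second randomization: change from Day 1 to cumulative week 24 (Protocol 5.4).
- Baseline: last value before the first dose after the second randomization (SAP 6.2.2 and 8.2), which is the week-24 recording.
- Primary endpoint: cumulative week 24 to week 36 (SAP 4.2.1).
- SAP 6.6 defines 603B analyses as those after randomization in 603B.

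None of these uses week 12, and visit 6 has no randomization. The recording does matter elsewhere. It is the 603A primary outcome, the integrated baseline for Seq 1 and 2 (SAP 6.2.1), and the 12-week integrated value for Seq 3 and 4 (SAP 4.3). Withholding the bottle restores none of these, because the value is already missing.

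**2. Repeat rule against validity rule.** The schedule in Protocol 6.11.1 gives 16 × 4 = 64 day and 8 × 2 = 16 night readings, 80 in all. The thresholds are 80% of these: 0.8 × 64 = 51.2, 0.8 × 16 = 12.8, 0.8 × 80 = 64. Counting all possible (day, night) pairs:

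- Protocol 6.10.2, day ≥ 51 and night ≥ 13: 14 × 4 = 56 pairs.
- SAP 8.1.1, total ≥ 64 and (day ≥ 51 or night ≥ 13): for k night readings there are k + 1 admissible day counts, so 1 + 2 + … + 17 = 153 pairs. The either/or clause never binds: with 64 or more in total, a day count of 50 or less forces at least 14 at night.
- Difference: 153 − 56 = 97 pairs that fail 6.10.2 but are valid in the SAP, for example 55 + 10 = 65, 60 + 10 = 70 or 50 + 16 = 66.

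The 97 are combinations, not a rate; the documents do not say how often each occurs.

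**3. The plan's sample size, reproduced.** Inputs from Protocol 9.2 are a 4 mm Hg difference, SD 15, two-sided 0.05 and 85% power. By normal approximation n = 2 × (1.960 + 1.036)² × 15² / 4² ≈ 252.5, so 253 per arm. The noncentral t gives 254, as stated. Completers: 680 × 0.75 = 510. At week 12: 680 × 0.92 = 625.6, stated as 626.

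**4. Effect on power.** Power = Φ(Δ / (σ√(2/m)) − 1.96), with m per arm. For 603B with m = 255: 4 / (15 × √(2/255)) = 3.011, and Φ(1.051) = 0.853. Suppose a proportion f of the 626 fail twice, all are lost, and the loss comes on top of the planned 25%, so that N = 510 × (1 − f):

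| Assumed f | 626 × f | 603B completers | 603B power |
|---|---|---|---|
| 0.5% | 3.1 | 507.4 | 0.852 |
| 1% | 6.3 | 504.9 | 0.850 |
| 2% | 12.5 | 499.8 | 0.846 |
| 3% | 18.8 | 494.7 | 0.843 |
| 5% | 31.3 | 484.5 | 0.835 |

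For 603A (5 mm Hg, SD 15), power is 0.986 with 313 per arm and 0.982 if 5% of values are missing.

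**The case against.** *Loss from 603B is an inference.* A reader might infer that every subject with two failures at week 12 is dropped. The documents do not say so. Protocol 6.11.1 contrasts screen failure before randomization with missing data after it, withdrawal is written only for week 24, and 3.1.2 starts 603B without a condition. Together these suggest that the subject may continue. What stands is that four places make the bottle conditional and none gives an exception.

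*The discarded recording depends on the repeat trigger.* The Protocol synopsis, Protocol 3.1.1 and SAP 3.5.1 call for a repeat only below 64 readings. Under that trigger, every replaced recording also fails the SAP's total and nothing usable is lost; 55 + 10 would not be repeated. This stands as a condition on the point. Against it, those sentences describe the baseline recording, and 6.10.2 states both minima. SAP 12 also reads the protocol rule as the stricter one. Had the protocol meant only the total, the SAP rule would match it exactly (all 153 pairs) and would have relaxed nothing.

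*Double failures are not the same as missing primary values.* A second set that fails the day-and-night minimum but has 64 or more readings is entered and is SAP-valid. A reader might take per-attempt failure rates of 5–20% and count 626p² = 1.6 to 25 subjects, or, with a within-subject correlation of 0.3, 626 × (p² + 0.3p(1 − p)) = 10.5 to 55, about 9% of 626. Those rates are assumptions. The count also overstates what can be recovered, which is only subjects whose first recording is SAP-valid and whose second is not.

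*The effect is small.* This stands. Even at that extreme (f = 0.088, N = 465.1), 603B power is about 0.82.

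**Conclusion.** The point holds as a minor one, in two parts.

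1. The dispensing condition and the missing-value rule conflict for a double failure at visit 6 and must be reconciled. For analysis, the success condition is needed only at visits 3 and 9, where the mean decides eligibility or balancing group.
2. If the day-and-night minimum in 6.10.2 governs repeats, the second-set-only rule can lose an SAP-valid recording and leave an avoidable missing value in the 603A primary endpoint, and likewise at weeks 24 and 36.

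Neither the failure rate nor the number of recoverable recordings can be found from the documents. At an assumed 0.5–5% of double failures, 603B power falls from about 0.853 to between 0.852 and 0.835. The documents do not support a claim that a material share of either study is lost. The case for change is consistency between sites and fewer missing primary values at almost no cost.

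**What to change.** 1. In Protocol 5.4, 6.10.2 and 6.11.1 and SAP 3.8.1, state that a double failure at visit 6 is recorded as missing and does not by itself prevent entry to 603B. Leave the condition at visits 3 and 9.
2. In Protocol 7, SAP 3.10 and SAP 6.4, enter both recordings in the CRF. Analyse the second if it is valid under SAP 8.1.1, otherwise the first if that is valid. State one repeat trigger throughout.
3. In SAP 6.2.1, for the integrated summaries, do not let a missing week-12 ABPM in Seq 1 or 2 fall back to Day 1 as the baseline. The last-non-missing rule would otherwise count change over 12 weeks of placebo as change on bexagliflozin, in what SAP 4.3 lists as secondary endpoints.

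The cost is short edits in the sections named, one IWRS setting, and entry of readings already downloaded. The drawback is that some 603B subjects will lack a week-12 ABPM, which affects the integrated summaries only. SAP 10 reports the interim analysis as done, so item 1 helps only subjects not yet past visit 6. For item 2, earlier first recordings may still be recoverable from source; any recovery should be specified before unblinding.
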